### **Patient Data Protection**

Patients will be assigned a unique identifier and will not be identified by name in electronic case report forms (eCRFs), trial-related forms, study reports, or any related publications. Patient and investigator personal data will be treated in compliance with all applicable laws and regulations. In the event the trial protocol, study report, or trial data are included in a public registry, all identifiable information from individual patients or investigators will be redacted according to applicable laws and regulations.

The patient must be informed that his/her personal trial-related data will be used by the sponsor in accordance with local data protection law. The level of disclosure must also be explained to the patient. The patient must also be informed that his/her medical records may be examined by sponsor or Contract Research Organization auditors or other authorized personnel appointed by the sponsor, by appropriate IRB/EC members, and by inspectors from regulatory authorities.

### **Disclosure**

All information provided regarding the trial, as well as all information collected and/or documented during the course of the trial, will be regarded as confidential. The investigator (or designee) agrees not to disclose such information in any way without prior written permission from the sponsor.

### **Data Quality Assurance**

The following data quality steps will be implemented:

- All patient data relating to the trial will be entered on eCRFs, unless directly transferred to the sponsor or designee electronically (e.g., laboratory data).
- All directly transferred data to the sponsor must be described in a Data Transfer Agreement (DTA) which must be signed by sponsor and the laboratory transferring data.

- The investigator must maintain accurate documentation (source data) and complete a source data list, defining where the specific source data that supports the information entered in the eCRF can be found.
- The investigator must permit trial-related monitoring, audits, IRB/EC review, and regulatory agency inspections and provide direct access to source data documents.
- The sponsor or designee is responsible for the data management of this trial including quality checking of the data. Predefined, agreed risks, monitoring thresholds, quality tolerance thresholds, controls, and mitigation plans will be documented in Xcelerate Risk and Issue Management system (XRIM). Additional details of quality checking to be performed on the data may be included in the data management plan and the data review plan.
- Trial monitors will perform ongoing source data verification to confirm that data entered into the eCRF by authorized site personnel are accurate, complete, and verifiable from source documents; that the safety and rights of patients are being protected; and that the trial is being conducted in accordance with the currently approved protocol and any other trial agreements, ICH GCP, data management plan, and all applicable regulatory requirements.
- Records and documents, including signed ICFs, pertaining to the conduct of this trial must be retained by the investigator in accordance with 21 CFR 312.62(c) (US sites) or in the trial site archive for at least 25 years after the end of the trial (European sites) unless local regulations or institutional policies require a longer retention period. No records may be destroyed during the retention period without the written approval of the sponsor. No records may be transferred to another location or party without written notification to the sponsor.

## Investigator Documentation Responsibilities

All individual, patient-specific trial data will be entered into a 21 CFR Part 11-compliant electronic data capture (EDC) system on an eCRF, containing edit checks on individual fields where deemed necessary, in a timely fashion. It is expected that data is entered in the eCRF within 5 working days; however, dosing and any AEs in Part 1 Cycle 1 should be entered within 24 hours. In case of data entry delay for Part 1 Cycle 1, the site is to confirm that the patient received the dose as per protocol and that any AEs (including DLTs) have been reported. All data generated from external sources (e.g., central laboratory, pharmacokinetics central readers) and transferred to the sponsor or designee electronically will be integrated with the patient's eCRF data in accordance with the data management plan and the applicable Data Transfer Agreements.

An eCRF must be completed for each patient who signs an ICF and undergoes any pre-screening or screening procedures, according to the eCRF completion instructions. The investigator will ensure that corrections are made to the eCRFs and that data queries are resolved in a timely fashion by the trial staff.

The investigator will sign and date the eCRF via the EDC system's electronic signature procedure. These signatures will indicate that the investigator reviewed and approved the accuracy of the data on the eCRF, the data queries, and the site notifications. The data will be considered clean and final upon signature from the investigator.

## Publications

If on completion of the trial the data warrant publication, the investigator may publish the results in recognized (refereed) scientific journals subject to the provisions of the clinical trial agreement (CTA). Unless otherwise specified in the CTA, the following process shall occur:

The institution and investigator shall not publish or present data from an individual trial center until the complete multicenter trial has been presented in full or for 2 years after the termination of the multicenter trial, whichever occurs first. Subsequent publications must refer to the multicenter findings. Thereafter, if the investigator expects to participate in the publication of data generated from this site, the institution and investigator shall submit reports, abstracts, manuscripts, and/or other presentation materials to the sponsor for review before submission for publication or presentation. The sponsor shall have 60 days to respond with any requested revisions, including (without limitation) the deletion of confidential information. The investigator shall act in good faith upon requested revisions, except the investigator shall delete any confidential information from such proposed publications. The investigator shall delay submission of such publication or presentation materials for up to an additional 90 days in order to have a patent application(s) file

## Appendix 3: Schedule of Assessments

**Table 6: Schedule of Assessments – Part 1, Screening and Cycle 1**

Dosing/Measurements/Evaluations	Screening	 Lu-DTPA-omburtamab Treatment Period  – Cycle 1				
	Day -29* to -1	Day 1	Day 8 (±1)	Day 15 (±1)	Day 22 (±1)	End-of-Cycle Visit (Day 29 [±1])
Informed consent 	X					
Eligibility check	X					
Demographics, height, body weight	X					
Medical, surgical, and disease history	X					
Prior/concomitant medications	X	X	X	X	X	X
Physical examination 	X					
Vital signs 	X	X	X	X	X	X
Performance test 	X 					
MRI of the brain and spine 	X 					
Neurological examination 	X	X				
Placement of indwelling ICV access device	X 					
ICV access device patency/CSF flow assessment	X					
Premedication (oral dexamethasone/IV equivalent) 		X	X			
Anti-pyretic and anti-histaminergic premedication 		X	X			
ICV  Lu-DTPA-omburtamab dosimetry dose		X				
ICV  Lu-DTPA-omburtamab treatment dose			X			
Whole-body planar gamma camera scan 		X 	X 	X 		
Blood and CSF for calculation of absorbed doses 		X 		X 		
Clinical chemistry and hematology 	X	X	X	X	X	X
CSF for cytology  , total protein, glucose, and cell count	X 					
Blood and CSF for culture		X 	X 			
Blood and CSF sampling for ADA 	X 					
Blood and CSF sampling for pharmacokinetics			X 	X 		
Pregnancy testing 	X	X	X			
Adverse events 	X	X		X	X	X

Abbreviations: ADA = anti-drug antibody; AE = adverse event; CSF = cerebrospinal fluid; ctDNA = circulating tumor deoxyribonucleic acid; EOT = end of treatment; HSA = human serum albumin; ICF = informed consent form; ICV = intracerebroventricular; IMP = investigational medicinal product; IV = intravenous; MRI = magnetic resonance imaging; NCI = National Cancer Institute; SAE = serious adverse event.

\* A longer screening period (e.g., due to logistics, COVID-19 situations etc.) are allowed; however, eligibility evaluation must be re-confirmed. Screening period of >60 days with individual patient considerations to be discussed with the sponsor.

 The Lu-DTPA-omburtamab Treatment Period is divided into 5-week cycles. In Part 1, the patient can receive up to 2 cycles at the discretion of the investigator. Cycle 1 starts with a dosimetry dose on Day 1 and continues with the first treatment dose on Day 8 (adjustments to the dosing schedule will be accommodated on a patient-by-patient basis depending on the clinical condition of the patient). The infusion reservoir must be flushed with HSA and CSF after each infusion. On dosing days, all assessments are done before dosing.

 If the IMP is discontinued after Cycle 1, the Day 29 Visit is replaced by the EOT Visit.

 Informed consent must be obtained before any trial-related procedures. If the indwelling ICV access device (e.g., Ommaya) is placed in connection with the tumor resection, the informed consent must be obtained prior to the surgery, and before the start of the screening period, unless this is placed as part of a standard of care procedure at site. If any procedures/tests are from before informed consent is obtained, it must be clear from source documents that this was not performed for the purpose of the present trial. In these cases, the procedures/tests do not need to be repeated at the Screening Visit if they were performed within the allowed timelines. The investigator is responsible for documenting this properly.

 Physical examinations to be performed at screening and as clinically indicated.

 Measurements of heart rate, respiratory rate, temperature, and blood pressure. On dosing days, measurements to be taken before and 30 min after the end of the IMP infusion.

 Lansky Scale <16 years, Karnofsky Scale ≥16 years.

 To be performed within 3 weeks prior to the first IMP infusion. May be performed on the first dosing day but it must be before IMP administration.

 MRI of the brain and spine will be completed before first IMP administration, at the EOT Visit (preferably ±4 days of the actual visit date). MRI can be performed on a separate day to the other visit assessments, if required, in accordance with investigational site standards.

 Will be used to evaluate safety and efficacy.

 Beginning 24 hours before IMP administration, divided into twice-daily doses for a total of 3 days.

 Given 1-2 hours prior to IMP administration, including oral acetaminophen/paracetamol and antihistamine (e.g., diphenhydramine).

 Following the dosimetry dose, whole-body planar gamma camera scans will be performed at 4 h (4-5 h), 24 h (22-26 h), 48 h (46-50 h), and Day 5-7 (may be performed on Day 8; however, must prior to the treatment dose), and on Day 15 (±12 hours), i.e., 7 days after administration of the treatment dose (see [Table 4](#)). SPECT imaging is optional at 24 h (22-24 h), 72 h (70-74), Day 5-7 (or Day 8 pre-dose), and on Day 15 (±1) (i.e., 7 days after the treatment dose).

 Approximately 0.5 mL of CSF and 2 mL of peripheral blood will be drawn at each timepoint (see [Table 4](#)), i.e., before treatment (baseline; to avoid withdrawing too high volumes of CSF on the day of the dosimetry dose, baseline sample should be drawn in the time between placement of the ICV access device and 1 day before dosing) and following the dosimetry dose at 30 min (±5 min), 1 h (±10 min), 4 h (±10 min), 24 h (±30 min), 48 h (±1 h) and 72 h (±4 hour). In addition, samples are drawn on Day 5-7 (may be on Day 8; however, must be prior to the treatment dose) and on Day 15 (±12 hr), i.e., 7 days after administration of the treatment dose.

 In accordance with [Appendix 1](#).

 If CSF cytology sample is positive, it must be repeated within 4 weeks of the positive sampling.

 Drawn and held for culture only if elevated body temperature after dosing suggests infection rather than expected response to ICV dosing. Samples to be taken within 6 hours after completion of IMP infusion.

 The baseline ADA samples must be drawn prior to the dosimetry dose and to avoid withdrawing too high volumes of CSF on the day of the dosimetry dose, the samples should be drawn in the time between placement of the ICV access device and 1 day before dosing. Serum and CSF samples for ADA analyses will be drawn at baseline and after last treatment. Presence of ADA will be analyzed at a central laboratory.

 Blood and CSF samples for pharmacokinetics will be drawn as per [Table 5](#). On Day 15 (i.e., 7 days after the treatment dose), blood collection only.

 Pregnancy testing (serum or urine) is mandatory for women of childbearing potential at screening, within one week prior to each dose, and at the EOT Visit.

 Non-serious AEs should be reported from the day of first IMP administration until 5 weeks after the patient's last dose of IMP. Non-serious AEs occurring between signing the ICF and the first IMP administration must be recorded as medical history. Serious AEs should be reported from signing the ICF until 5 weeks after the patient's last dose of IMP. Thereafter and during the follow-up period, only SAEs or Grade 3 or higher AEs at least possibly related to Lu-DTPA-omburtamab or to the presence of the indwelling catheter system should be reported until end of trial. In the post-trial monitoring period, new onset of cancers, regardless of causality, should be reported.

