### ***3.1.1.2. Definition of Dose-limiting Toxicity***

DLTs are defined as AEs (graded according to CTCAE version 5) occurring within 5 weeks after first IMP administration in Cycle 1 of Part 1 and that are considered possibly or probably related to IMP and meet any of the following criteria:

- Grade 4 myelosuppression (i.e., anemia, thrombocytopenia, or neutropenia) lasting more than 1 week, or more than 3 weeks following intervention (e.g., blood transfusion or granulocyte-macrophage colony-stimulating factor [GM-CSF])
- Any other Grade 4 hematological AE
- Grade  $\geq 3$  thrombocytopenia associated with bleeding
- Grade  $\geq 3$  febrile neutropenia (i.e., fever concurrent with neutropenia) lasting more than 5 days despite use of growth factors and antibiotics
- Grade 4 infusion-related reactions/anaphylaxis
- Grade 3 infusion-related reactions (excluding fever and Grade 3 abnormal laboratory values) that do not resolve to Grade  $\leq 1$  within 5 days of onset.
- Any non-hematological Grade  $\geq 3$  AE that is not listed in the list of exemptions below

DLTs must be entered onto the clinical AE report form and be reported from site to sponsor within 24 hours of the investigator's first knowledge of the event (see [Section 7.4.5.2](#)). If any of the side effects mentioned in the DLT definitions occur during Cycle 2 in Part 1, these will be discussed at the first upcoming preplanned DMC meeting, and the Sponsor Safety Committee will evaluate the DMC recommendations for further dosing.

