##### **4.3.2. End of Treatment**

The end of treatment (EOT) is defined as the day the last dose of Lu-DTPA-omburtamab is received. The EOT Visit should occur 5 to 6 weeks after the last dose, whether this is a premature treatment discontinuation or treatment completion.

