### 8.2. Analysis Populations

The following analysis sets will be included for this trial:

**Safety Analysis Set:** will consist of all patients who received at least 1 dose of trial treatment (treatment dose or dosimetry dose).

**DLT Evaluable Analysis Set:** will include patients in the dose escalation who as a minimum is evaluated during the 5 weeks DLT evaluation period, or who has a DLT during the DLT evaluation period. This analysis set is a subset of the Safety Analysis Set.

**Full Analysis Set (FAS):** will consist of all patients in the Safety Analysis Set.

**Dosimetry Analysis Set (Part 1 only):** will consist of all patients who received the dosimetry dose and have evaluable data for absorbed doses to CSF and blood or for whole-body planar scan.

**PK Analysis Set:** will consist of all patients who received at least 1 treatment dose of trial drug and have evaluable PK data.

Efficacy will be analyzed using the FAS. Safety will be analyzed using the Safety Analysis Set. Dosimetry and absorbed doses to CSF and blood will be analyzed using the Dosimetry Analysis Set. Pharmacokinetics will be analyzed using the PK Analysis Set.

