## **8.5. Safety Analysis**

### **8.5.1. Dose-Limiting Toxicities**

DLTs observed during the DLT evaluation period, i.e., within 5 weeks after the dosimetry dose in Cycle 1 of the dose escalation will be listed and summarized by Medical Dictionary for Regulatory Activities (MedDRA) system organ class (SOC) and preferred term (PT). DLTs observed outside the DLT evaluation period will be presented in a listing. The information from

the DLTs will be used to guide the escalation and ultimately determine the MTD. Furthermore, the information will be used to make recommendations regarding the RP2D. The evaluation of DLTs will be based on the DLT evaluable analysis set.

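### Part 1 patients who stop between the Day 8 dose and Day 29 without a DLT have no guaranteed scheduled blood count after Day 22, although the DLT window runs to about Day 36

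*Combined protocol and SAP*

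**What the plan says.** **DLT window.** Section 3.1.1.2 counts events "occurring within 5 weeks after first IMP administration in Cycle 1 of Part 1". Section 8.5.1 uses the same anchor: "within 5 weeks after the dosimetry dose in Cycle 1 of the dose escalation".

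**Dosing.** Table 6, footnote 1: "Cycle 1 starts with a dosimetry dose on Day 1 and continues with the first treatment dose on Day 8". If no Cycle 2 is given, the Day 8 treatment dose is the last dose.

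**Scheduled counts.** Table 6 marks clinical chemistry and hematology at screening and on Days 1, 8, 15, 22 and 29. Footnote 2 then says: "If the IMP is discontinued after Cycle 1, the Day 29 Visit is replaced by the EOT Visit". Table 7, footnote 2, has the Cycle 2 visits skipped for the same patients, which also removes the count on Day 1 of Cycle 2.

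**EOT timing.** Section 4.3.2: "The EOT Visit should occur 5 to 6 weeks after the last dose, whether this is a premature treatment discontinuation or treatment completion". Section 3.1.1 gives the same interval for Part 1. Three other places point to an earlier visit. Section 4.3.5 wants discontinued patients seen at EOT promptly. Section 4.3.2.1 treats the EOT Visit as the data collection made when treatment is discontinued. Section 5.3.1 asks for the EOT assessments when a Part 1 patient would need a dose reduction. None of the three fixes a day.

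**Evaluability.** Without a DLT, a patient enters the DLT Evaluable Analysis Set (Section 8.2) if he or she is one "who as a minimum is evaluated during the 5 weeks DLT evaluation period". No minimum coverage by blood counts is stated.

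**The concern.** Patients who go on to Cycle 2 have counts on Day 29 and, if Cycle 2 starts on time, at about Day 36. Patients who stop early can lose both, so the end of the DLT window is watched less closely in them than in the others at the same dose level.

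The hematological DLT most exposed is Grade 4 myelosuppression lasting more than a week (Section 3.1.1.2). Without symptoms it can be seen only on a blood count. Cytopenia is the main known toxicity of the iodine-131 product: Section 1.2.1 reports at least one cytopenia-related event in 81.7% and 87.5% of patients in its two trials. Section 5.3.1 itself foresees Grade 3 or 4 myelosuppression still present in the fifth week of a cycle, and Day 29 is the scheduled Cycle 1 visit that begins that week.

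Escalation turns on very small counts (Section 3.1.1.1). With no DLT in 3 patients the dose rises, and with one the level is expanded. With one in 6 the dose rises, and with two it stops. A single unseen DLT could change a decision. Under Section 4.4 the DMC reviews a level once its last patient has completed Cycle 1, so an EOT count on Day 43 or later may come after that review.

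**Working it through.** **Day convention.** Table 6 describes Day 15 as 7 days after the Day 8 treatment dose: 8 + 7 = 15. Table 8, footnote 1, starts Cycles 2 to 5 on Days 36, 71, 106 and 141, which is 1 + 35k for k = 1 to 4. Both agree with calendar day = dose day + elapsed days.

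**Close of the DLT window.** 1 + 35 = Day 36 (Day 35 if Day 1 is counted as the first of the 35 days).

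**EOT Visit under Section 4.3.2, last dose on Day 8.**
- Earliest: 8 + 35 = Day 43. Latest: 8 + 42 = Day 50.
- With the ±1 day allowed on the treatment dose: 7 + 35 = Day 42 to 9 + 42 = Day 51.
- Distance past the window: 43 − 36 = 7 days to 50 − 36 = 14 days.

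**Uncovered time when footnote 2 applies.**
- Last remaining scheduled count: Day 22 (21 to 23 with the visit window).
- Uncovered in-window days: 36 − 22 = 14, that is Days 23 to 36. The range is 12 (35 − 23) to 15 (36 − 21).
- In-window days after the treatment dose: 36 − 8 = 28, so the uncovered share is 14 of 28.
- Interval between scheduled counts: 43 − 22 = 21 days to 50 − 22 = 28 days.

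**What can fall in the gap.** Take 8 days as the shortest Grade 4 episode lasting more than a week.
- Counts on Day 22 and Day 43: an onset on any of Days 23 to 35 meets no scheduled count (onset on Day 35 ends on Day 42).
- Counts on Day 22 and Day 50: an onset on any of Days 23 to 36 meets none.
- With EOT on Day 43, an episode of up to 20 days (Days 23 to 42) fits wholly in the gap.

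**With Day 29 kept.** The uncovered end is 36 − 29 = 7 days. With EOT on Day 43, an 8-day episode is missed only if it starts on Days 30 to 35.

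**Who is affected.**
- Discontinuation decided after the Day 8 dose and before Day 29: the figures above apply.
- Discontinuation decided after Day 29 has been attended: that count exists, and about 7 days are uncovered.
- Dosimetry dose only: EOT would be 1 + 35 = Day 36 to 1 + 42 = Day 43, and these patients are replaced under Section 4.3.4. The Day 43 to 50 figure does not describe them.

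**The case against.** The strongest reply is that Day 43 to 50 is not settled. Sections 4.3.2.1, 4.3.5 and 5.3.1 can be read as placing the EOT Visit, which includes hematology (Table 7), at or soon after discontinuation. Replacing Day 29 would then move the count very little. This stands as a conflict in the text, but it does not close the gap. Section 4.3.2 expressly covers premature discontinuation, and the other sections name no day. An early EOT could also come before Day 29 and still replace it: an EOT on Day 23 would leave 36 − 23 = 13 days uncovered.

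Three stronger readings are tempting, and the documents do not support them.

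- *Everyone who stops after Cycle 1 loses the Day 29 count.* A patient who stops after attending Day 29 already has it.
- *Duration-based DLTs cannot be established in these patients.* Sections 4.3.5 and 7.4.5.5 require treatment-related Grade 3 or higher events, and all SAEs and DLTs, to be followed until resolved or judged chronic or stable. A related Grade 4 count seen on Day 15 or Day 22 must therefore be pursued. Only a cytopenia first arising after Day 22 is left exposed.
- *Patients stopping for toxicity go uncounted, so the MTD is biased upwards.* A DLT in Cycle 1 is itself a reason to stop (Section 4.3.2.1), and those patients are already counted. The exposed patients stop for other reasons, such as progression or their own decision. No passage shows that they carry more unseen toxicity. A patient judged not evaluable leaves the DLT set and is not counted as DLT-free, so both harms cannot apply to one patient.

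The other safeguards are partial. Section 7 allows unscheduled samples but does not require them. Adverse events are reported until 5 weeks after the last dose (Day 43 here), but that does not oblige anyone to take a blood count. Under Section 4.3.4, replacement after discontinuation unrelated to IMP is optional, and after a related event the DMC is consulted.

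**Conclusion.** The point holds in limited form. Read with Section 4.3.2, footnote 2 leaves no guaranteed scheduled blood count after Day 22 in a Part 1 patient who received the Day 8 dose and whose discontinuation, for a reason other than a DLT, is decided before Day 29. Up to 14 of the 28 in-window days after the treatment dose are then uncovered. The consequence is a possible missed Grade 4 cytopenia of late onset, in a patient who may still be counted as DLT-free in a decision based on 3 to 6 patients.

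This assumes nominal visit days, a window closing at Day 36 and EOT timed by Section 4.3.2. The documents do not say how many patients will stop in this interval or how often Grade 4 cytopenia would begin after Day 22, so neither the probability of a missed DLT nor any effect on the MTD can be calculated. The affected group is probably small. The change is still worth making, because the number of DLTs is the Part 1 primary endpoint and the correction is cheap.

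**What to change.** Delete the replacement in Table 6, footnote 2. Keep the Day 29 visit, with hematology, for every patient who received a Cycle 1 treatment dose, and make the EOT Visit an additional visit. Reconcile the EOT timing in Sections 4.3.2, 4.3.2.1, 4.3.5 and 5.3.1 so that one timing applies to patients who discontinue.

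This reduces the uncovered end of the window from 14 days to about 7 (Day 29 to Day 36) but does not close it. A further count on about Day 36 would close it, but that would be an extra sample for these patients, for the sponsor to weigh separately.

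The cost is one footnote, some consistency edits, and one already-defined visit retained for the few patients who stop early. Dosing and stopping rules are untouched.
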